APPENDIX B— Supplemental TRANSPLANTATION /OTHER APPENDICES

- 12.3 Used Scores and Scales
 - 12.3.1 Oswestry Low Back Pain Disability Questionnaire modified according to Hudson-Cook (OPDQ) and calculated as the Oswestry Disability Index (ODI)
 - 12.3.2 VAS (pain)
 - 12.3.3 SF-36, (United States) version

CONFIDENTIAL	Clinical Protocol DATE		Pa	age
99111 12 E111111 12		9Dec2019		
	mented Disc Regeneration in the $\underline{\mathbf{T}}$ reatment of th or without Intervertebral Disc Herniation –	WRITER TG, DB, PW	NO. 59	REV 6

1 ABBREVIATIONS

Abbreviation	Definition
AE	Adverse Event
BBA	Boston Biomedical Associates
CRF	Case Report Forms
ITT	Intent-To-Treat Population
LOCF	Last Observation Carried Forward
MITT	Modified Intent-To-Treat Population
MRI	Magnetic Resonance Imaging
ODI	Oswestry Disability Index
РР	Per-Protocol Population
РТ	Preferred Term
SAE	Serious Adverse Event
SAP	Statistical Analysis Plan
SOC	System Organ Class
SF-36	Short Form 36
VASPI	Visual Analogue Scale of Pain Intensity

2 SUMMARY

TITLE	Viable Allograft Supplemented Disc Regeneration in the Treatment of Patients with Low Back Pain with or without Intervertebral Disc Herniation					
DDEEACE	This Statistical Analysis Dlan (SAD) describes the planned analysis and reporting					
PREFACE	This Statistical Analysis Plan (SAP) describes the planned analysis and reporting					
	For vivex Biologics, inc protocol vAS1-001-017 (viable Allografi Supplemented					
	Disc Regeneration in the Treatment of Patients with Low Back Pain with or					
	without Intervertebral Disc Herniation). This study is being completed to assess					
	the safety and efficacy of viable allograft transplantation for the treatment of					
	patients with symptomatic disc degeneration and tissue loss.					
	The following documents were reviewed in preparation of this SAP					
	Clinical Passarah Protocol VAST 001 017 issued 11MAV2018					
	 Case report forms (CDEs) issued 16 A DD 2019 for Drotocol VAST 001 017 					
DUDDOGE	Case report forms (CKFs) issued for Protocol VAST-001-017.					
PURPOSE	The purpose of this SAP is to outline the planned analyses in					
	support of the Clinical Study Report (CSR) for protocol VAST-001-017.					
	Exploratory analyses not necessarily identified in this SAP may be performed to					
	support the clinical development program. Any post-hoc, or unplanned, analyses					
	not identified in this SAP will be clearly identified in the respective CSR.					
STUDY	To evaluate the safety and efficacy of viable allograft transplantation for the					
OBJECTIVES	treatment of patients with symptomatic disc degeneration and tissue loss.					
STUDY DESIGN	A multi-center, prospective, randomized, parallel-arm study composed of a					
	screening phase and an active phase.					
	In the screening phase subjects will be assessed for study eligibility via X-ray and					
	MRI and baseline SF-36. Oswestry Disability Index (ODI), and Visual Analogue					
	Scale of Pain Intensity (VASPI) will be established.					
	In the active phase, subjects who meet eligibility in the screening phase and meet					
	Active Phase entry criteria will be randomized to receive viable allograft placebo					
	as saline, or he assigned to continue conservative care treatment. All subjects will					
	as same, or or assigned to continue conservative care treatment. All subjects will return at 6 and 12 months for efficacy and safety assessments. Subjects randomized					
	to the conservative care arm will also be evaluated at 2 months, during which they					
	to the conservative care and will also be evaluated at 3 months, during which they are aligible to reacive visible allograft					
	The first 24 subjects randomized (at least 4 in each treatment group) will have an					
	additional study visit at 1 month after treatment. All data from the 1-month study					
	visit will be reviewed by the Steering Committee to confirm enrollment may					
	continue.					
ENDPOINTS	The study's co-primary endpoints are:					
	• Improvement in the ODI at 12 months after treatment					
	 Improvement in the VASPI at 12 months after treatment 					
	· Improvement in the VIISFF at 12 months after freatment					
	The study's secondary and points are:					
	In survey a secondary enupoints are.					
	• Improvement in the ODI and VASPI at 6 months after treatment					
	• Improvement in SF-36 at 6 and 12 months after treatment					
	• MRI measurements at 6 and 12 months after treatment					
	• Adverse Event (AE)/ Serious Adverse Events (SAE) rates after treatment					
	Hospitalization rate at 12 months after treatment					
	• Re-operation rate at 12 months after treatment					
	• Resource utilization following treatment at 6 and 12 months after treatment					

INTERIM	For safety and efficacy reasons, interim analyses are planned to be performed after						
ANALYSES	the first 24 subjects have completed the Month 1 assessment of the Active Phase.						
	This analysis will be performed in a descriptive manner only and no un-blinding						
	will occur unless a safety signal is evident. A Steering Committee will be conve						
	to review the results of the interim analysis. A similar review will occur when the						
	complete the Month 6 assessment of the Active Phase, where primary endpoints of						
	pain and ODI, and randomized MRI will be available for analysis.						
FINAL ANALYSES	All final analyses identified in this SAP will be completed after the last subject has						
	completed the 12-month follow-up visit.						
	The co-primary endpoints will be tested using the Kruskal-Wallis test to compare						
across the three treatment groups at a two-sided α =0.05 level. If the overal							
significant, the Dwass, Steel, Critchlow-Fligner method will be use							
	pairwise comparisons, while controlling for the overall familywise error level.						
	Both of the co-primary endpoints need to meet statistical significance for the						
	trial to be considered a success.						
	Secondary outcomes will be analyzed in an exploratory way at a two-sided $\alpha=0.05$						
	level without controlling for multiple testing						
	Teres, traiout controlling for multiple tosting.						

3 Study Objectives and Endpoints

3.1 STUDY OBJECTIVE

The objective of this study is to evaluate the safety and efficacy of viable allograft transplantation for the treatment of patients with symptomatic disc degeneration and tissue loss.

3.2 STUDY ENDPOINTS

3.2.1 CO-PRIMARY ENDPOINTS

The study's co-primary endpoints are:

- Improvement in the ODI at 12 months after treatment
- Improvement in the VASPI at 12 months after treatment

3.2.2 SECONDARY ENDPOINTS

The study's secondary endpoints are:

- Improvement in ODI and VASPI at 6 months after treatment
- Improvement in the SF-36 at 6 and 12 months after treatment
- MRI measurements at 6 and 12 months after treatment
- Adverse Event (AE)/ Serious Adverse Events (SAE) rates after treatment
- Hospitalization rate at 12 months after treatment
- Re-operation rate at 12 months after treatment
- Resource utilization following treatment at 6 and 12 months after treatment
- Changes in laboratory tests

4 SAMPLE SIZE

The primary criteria will be analyzed using Wilcoxon rank-sum-test. Based on Fairbanks, 2000¹, Hudson-Cook, 1989² and Fritz, 2001³ a common standard deviation of $\sigma = 15.5$ score points can be assumed.

Fritz, 2001, calculated a Minimum Clinically Important Difference of 6 score points. Reliability is reported in the literature in the range of 0.75 - 0.91. Worst case, using the standard deviation above results in a measurement error of 7.75 score points. Thus, we assume a clinically relevant difference of 9 score points. Under this assumption, the probability p (x < y) = 0.341 (x, y observations in the groups, respectively). A sample size of 40 in each group will have 80 % power to detect with a probability of 0.341 that an observation in one group is less than an observation in the other group using Wilcoxon rank-sum-test with a 0.05 two sided significance level (calculations were done using nquery 4.0).

Approximately 220 subjects randomized to viable allograft or placebo or control in 3.5:1:1 ratio:

Active Allograft = 140 Placebo = 40 Conservative Care = 40

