13.3 Sample Size Considerations

The primary criteria will be analyzed using Wilcoxon rank-sum-test. Based on Fairbanks, 2000^{51} , Hudson-Cook, 1989^{36} and Fritz, 2001^{52} a common standard deviation σ = 15.5 score points can be assumed.

Fritz, 2001, calculated a Minimum Clinically Important Difference of 6 score points. Reliability is reported in the literature in the range of 0.75 - 0.91. Worst case using the standard deviation above results in a measure error of 7.75 score points. Thus, we assume a clinically relevant difference of 9 score points. Under this assumption the probability p (x < y) = 0.341 (x, y observations in the groups, respectively). A sample size of 40 in each group will have 80 % power to detect a probability of 0.341 that an observation in one group is less than an observation in the other group using Wilcoxon rank-sum-test with a 0.05 two sided significance level (calculations are done using nquery 4.0).

CONFIDENTIAL	Clinical Protocol	DATE	P	age
		9Dec2019		
	mented Disc Regeneration in the Treatment of the or without Intervertebral Disc Herniation –	WRITER TG, DB, PW	NO. 45	REV 6

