9.1 CO-PRIMARY EFFICACY ENDPOINTS

The co-primary endpoints are the change in ODI and VASPI at 12 months after treatment.

The hypothesis for the ODI is as follows:

H₀: $\tilde{x}_1 = \tilde{x}_2 = \tilde{x}_3$ H_a: at least one median is not equal

Where \tilde{x}_1 is the median pre-post difference in the active allograft group, \tilde{x}_2 is the median pre-post difference in the placebo group and \tilde{x}_3 is the median pre-post difference in the conservative care group.

The null hypothesis (H_0) for this endpoint states that there is no difference in change in ODI at 12 months between the three treatment groups (1) Active Allograft, (2) Placebo, and (3) Conservative Care. The alternative hypothesis (H_a) is that there is a difference in change in ODI at 12 months between the three treatment groups.

The hypothesis for the VASPI is as follows:

 $\begin{array}{l} H_0: \ {\tilde x}_1 = {\tilde x}_2 = {\tilde x}_3 \\ H_a: \ at \ least \ one \ median \ is \ not \ equal \end{array}$

Where \tilde{x}_1 is the median pre-post difference in the active allograft group, \tilde{x}_2 is the median pre-post difference in the placebo group and \tilde{x}_3 is the median pre-post difference in the conservative care group.

The null hypothesis (H₀) for this endpoint states that there is no difference in change in VASPI at 12 months between the three treatment groups (1) Active Allograft, (2) Placebo, and (3) Conservative Care. The alternative hypothesis (H_a) is that there is a difference in change in VASPI at 12 months between the three treatment groups.

For both the ODI and the VASPI, the pre-post difference of the groups will be compared using the Kruskal-Wallis test at a two-sided α -level of 0.05. If the result for either test is significant, then the Dwass, Steel, Critchlow-Fligner Method will be used to assess all pairwise comparisons for that endpoint.

Both the ODI and the VASPI need to be statistically significant (p<0.05) for the trial to be a success.

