13 CHANGES IN THE PLANNED ANALYSIS

Section	Description	Justification
3.2.1 Co-primary	The primary endpoint is now a	The protocol inconsistently stated what the
endpoints	co-primary endpoint of the ODI	primary endpoint would be. It stated the ODI and
	and VASPI at 12 months.	VASPI at 6 and 12 months, but the primary
		analyses and powering was for the ODI at 12
		decided it would be a constructed of the way
		both endpoints would need to be met for the trial
		to be considered a success
3.2.2 Secondary	The ODI and VASPI at 12	The protocol repeated the primary endpoints in
endpoints	months was removed as a	the secondary endpoint section. The primary
-	secondary endpoint.	endpoints were removed from the secondary
		endpoint section.
6 Analysis	The mITT population will be the	The protocol summary stated the main analysis
Populations	primary analysis population for	would occur in the mITT population. The body
	efficacy and safety.	of the protocol stated analyses would occur in the
		written it was decided the mITT population
		would be used for the primary analyses and
		endpoints would also be run in the PP
		population.
7.3 Methods for	The primary analysis will be	The protocol summary did not indicate LOCF,
Withdrawals,	completed using available data.	but the body of the protocol noted the use of
Missing Data, and	A sensitivity analysis will be	LOCF. At the time this SAP was written it was
Outliers	performed using LOCF.	decided the primary analysis would occur in
		those with available data, and LOCF would be
		nopulation
9.1 Primary Efficacy	The primary efficacy analysis	The Kruskal-Wallis test is being used in place of
Endpoints	will be in the ODI and the	the Wilcoxon Rank Sum test as it is the
-	VASPI at 12 months. The	appropriate test for a three-group comparison,
	Kruskal-Wallis test will be used	where the Wilcoxon Rank Sum test is the
	in place of the Wilcoxon Rank	equivalent test for a two-group comparison. The
	Sum test. If the result is	addition of the Dwass, Steel, Critchlow-Fligner
	Critchlow Eligner Method will	evaluate which comparisons are significantly
	be used to assess all pairwise	different. The originally proposed responder
	comparisons. A responder	analysis was removed since it had the potential
	analysis that was initially	for results to be clinically incompatible due to
	described in the protocol was	the use of the Bonferroni-Holm procedure (e.g. a
	removed.	difference of 1 could be significant, but a

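### The stated 80% power for 40 per group is about 70% on the plan's own inputs, and SAP section 4 gives no power for the Kruskal-Wallis rule that decides success

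*SAP*

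**What the plan says.** Protocol 13.3 takes an SD of 15.5 points, a relevant difference of 9 points and the resulting p(x<y) of 0.341, and concludes: "A sample size of 40 in each group will have 80 % power to detect a probability of 0.341", using a Wilcoxon rank-sum test at two-sided 0.05. SAP section 4 carries the same calculation over almost unchanged ("A sample size of 40 in each group will have 80 % power to detect with a probability of 0.341"). It opens with "The primary criteria will be analyzed using Wilcoxon rank-sum-test" and ends with the allocation "Active Allograft = 140 Placebo = 40 Conservative Care = 40".

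SAP 9.1 specifies a different analysis. For ODI and for VASPI, "the pre-post difference of the groups will be compared using the Kruskal-Wallis test at a two-sided" level of 0.05, followed by Dwass-Steel-Critchlow-Fligner (DSCF) pairwise comparisons if the overall test is significant. The success rule is: "Both the ODI and the VASPI need to be statistically significant (p<0.05) for the trial to be a success".

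SAP section 13 records the change ("The Kruskal-Wallis test is being used in place of" Wilcoxon). It also says of the protocol that the primary "analyses and powering was for the ODI at 12" months. It does not revisit the 80%.

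**The concern.** The 80% is the only power figure in either document. Two things are wrong with it.

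- It does not follow from the inputs printed beside it.
- It describes a two-group test at 40 v 40 on one endpoint, whereas success depends on a three-group test at 140/40/40 on two endpoints.

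A reader weighing a null result would rely on this figure. For saline against conservative care, the one comparison that really is 40 v 40, it is about 10 percentage points too high. For the rule that decides the trial there is no figure, no assumed VASPI effect, no ODI-VASPI correlation and no allowance for missing data.

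**Working it through.** **Inputs (SAP section 4, same in Protocol 13.3).** Difference 9, SD 15.5, p = 0.341, n = 40 per group, two-sided alpha 0.05, Wilcoxon rank-sum.

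**What reproduces.** For normal data p = Φ(−9/(15.5·√2)) = 0.3407, matching 0.341. The measurement error 15.5·√(1 − 0.75) = 7.75 also matches.

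**What does not.** Noether's formula is power = Φ(√(12·c(1−c)·N)·|p − 0.5| − z), where c is the share of the total N in one group.

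- Two-sided, 40 v 40: √(12·0.25·80) = 15.49; 15.49·0.159 = 2.463; Φ(2.463 − 1.960) = **69.3%**.
- Simulated Wilcoxon test on normal data: **70-71%**.
- Other two-sided approximations: 69.9% (variance under the alternative), 71.8% (efficiency-adjusted z), 72.7% (t test), 73.8% (z test on means). None comes near 80%.
- Sample size for 80%: (1.960 + 0.842)²/(6·0.159²) = 51.7 per group. Simulation gives about 80% at 50 and 81-82% at 52.
- One-sided 0.05: Φ(2.463 − 1.645) = 79.3%, and 80% needs 40.8 per group. The stated figure is therefore close to a one-sided result, though the text says two-sided.
- With 40 per group and two-sided 0.05, 80% power needs p = 0.5 − 2.802/√240 = 0.319, a shift of about 10.3 points instead of 9.

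**Allograft v one control, unadjusted.** For 140 v 40, √(12·(140/180)·(40/180)·180) = 19.32 and Φ(19.32·0.159 − 1.960) = 86.7%; simulated, about 88%.

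**The actual rule (illustrative).** Simulation, 20,000 runs per row, normal data, SD 15.5, with DSCF read only after a significant Kruskal-Wallis (KW) test. The documents do not supply these assumptions: VASPI has the same standardised effect as ODI (9/15.5 = 0.58), the correlation between endpoints is 0 to 0.7, and missing data are either nil (140/40/40) or 15% (119/34/34). Cells show complete data / 15% missing.

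| Month-12 scenario | KW, ODI | KW, both endpoints | Allograft v saline, DSCF, per endpoint |
|---|---|---|---|
| Allograft 9 better than both controls | 96% / 92% | 92-93% / 85-88% | 78-79% / 70% |
| Saline equals allograft; conservative care 9 behind | 82% / 75-76% | 68-74% / 57-65% | no true difference |
| Saline 9 behind; conservative care 4.5 behind | 84% / 76-77% | 71-76% / 59-66% | 77-78% / 69% |
| Saline 9 behind; conservative care equals allograft | 82-83% / 75-76% | 68-74% / 57-66% | 77% / 69% |

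As a check, at zero correlation the two-endpoint figure should be near the square of the single-endpoint one: 0.823² = 0.677, against 0.679 simulated.

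The last two rows reflect something in the plan. Protocol 7.1.4 and 8.4 let conservative-care subjects receive allograft after month 3, and SAP 6.2 analyses them as randomised, so a full 9-point gap from that arm at month 12 cannot be taken for granted. The sizes used (gap halved or gone) are assumptions.

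**The case against.** The strongest reply is that little depends on the figure. The trial is about allograft, and those comparisons are 140 v 40, with about 87-88% unadjusted power. SAP section 13 openly replaces Wilcoxon with Kruskal-Wallis and SAP 9.1 is unambiguous, so no estimate, test or decision changes. The SAP was signed on 30 January 2020, when its section 13 reports imaging already collected, so a new power table cannot affect the design. Most of the scenario figures rest on assumptions from outside the plan. Protocol section 6 speaks of evaluable patients, Protocol 6.10 re-uses the assignments of untreated subjects, and SAP 11.1 adds a sensitivity analysis by treatment received.

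Much of this stands. The error does not show an underpowered trial, and the scenario figures are only illustrative. Protocol section 6 does bear on the 15% missing case, although evaluable is not defined there and loss before month 12 remains possible. A one-sided calculation is only a likely source of the 80%: an SD of about 13.5, or a shift of about 10.3, would also give it, and the software output is not shown.

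Three things are left unanswered. The 69-71% needs no assumption beyond the plan's own inputs. Section 13 discloses the new test but neither corrects the 80% nor gives power for the new rule. And 140 v 40 by an unadjusted rank-sum test is not the success criterion, nor is its power stated anywhere in the plan.

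**Conclusion.** The stated power is wrong as written. With the plan's own difference, SD, alpha, sidedness and test, 40 per group gives about 70%, not 80%. That conclusion is firm and does not depend on the scenarios.

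SAP section 4 also names a test that SAP 9.1 does not use for the primary analysis, and the operative rule has no stated power. Across the illustrative scenarios, power to win on both endpoints runs from 68% to 93% with complete data and from 57% to 88% with 15% missing. It depends mainly on whether one or both control arms trail allograft by 9 points, and on the assumed equal standardised effect for VASPI and the correlation of 0 to 0.7. No single figure should replace the 80%. The fault lies in the stated figure and the named test; the analysis in SAP 9.1 is clear.

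**What to change.** 1. In SAP section 4 and Protocol 13.3, withdraw the 80% or correct it. Possible text: *For placebo v conservative care, with 40 subjects per arm, the two-sided 0.05 Wilcoxon rank-sum test has about 70% power at p(x<y) = 0.341.*
2. In SAP section 4, delete the sentence naming Wilcoxon for the primary criteria and refer to section 9.1.
3. In SAP section 4, add a short table of power at 140/40/40, given as a range over scenarios: Kruskal-Wallis per endpoint, both endpoints, and allograft v saline after DSCF. The sponsor should supply and label its own assumptions for the VASPI effect, the ODI-VASPI correlation, missing data and crossover. At least one scenario should have saline equal to allograft, and one should have crossover narrowing the conservative-care gap. The most favourable figures (96% for one endpoint, 92-93% for both) should not stand alone as the headline.

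The cost is a few sentences and one table. The downside is a lower stated figure for 40 v 40 and an open statement that the two-endpoint rule falls below 80% in some scenarios. At this stage the correction documents power and may come too late to affect sample size. No change to enrolment or to the success rule is proposed.

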5 SEQUENCE OF PLANNED ANALYSES

5.1 INTERIM ANALYSES

For safety and efficacy reasons, interim analyses are planned to be performed after the first 24 subjects have completed the Month 1 assessment of the Active Phase. This analysis will be performed in a descriptive manner only and no un-blinding will occur unless a safety signal is evident. A Steering Committee will be convened to review the results of the interim analysis. A similar review will occur when they complete the Month 6 assessment of the Active Phase, where primary endpoints of pain and ODI, as well as randomized MRI will be available for analysis.

There are no other planned interim analyses for this study.

5.2 FINAL ANALYSES AND REPORTING

All final, planned, analyses identified in the protocol and in this SAP will be performed only after the last subject has completed the 12-month visit after treatment. Key statistics and study results will be made available following database lock. Any post-hoc, exploratory analyses completed to support planned study analyses, which were not identified in this SAP, will be documented and reported as necessary. Any results from these unplanned analyses will also be clearly identified as post-hoc analyses.

6 ANALYSIS POPULATIONS

6.1 INTENT TO TREAT POPULATION (ITT)

The intent-to-treat (ITT) population for this study includes all enrolled subjects. Subjects are considered enrolled in the trial after they have signed the informed consent form, all screening procedures were

performed, and eligibility for the study was confirmed. Subjects are analyzed under the treatment to which they were randomized.

6.2 MODIFIED INTENT TO TREAT POPULATION (MITT)

The modified intent-to-treat population (mITT) includes all ITT subjects who underwent treatment and had at least one valid post-treatment assessment of the ODI and VASPI. This mITT population is the primary analysis population for efficacy analyses. Subjects are analyzed under the treatment to which they were randomized.

